4.3 Control Arm

Parents randomised into the control arm will receive signposting to LBTH and voluntary sector welfare benefits advice service, national websites and helplines.

4.4 Unblinding

Participants and researchers are unblinded. Statisticians and health economists will remain blinded until after database lock and primary analysis has been completed. An unblinded statistician will be appointed when required to support the oversight of the trial.

4.5 Protocol Intervention Discontinuation

In consenting to the trial, participants are consenting to the trial intervention, trial follow-up and data collection.

As participation in the trial is entirely voluntary, the participant may choose to discontinue the trial intervention at any time without penalty or loss of benefits to which they would otherwise be entitled. Although not obliged to give a reason for discontinuing their trial intervention, a reasonable effort should be made to establish this reason, whilst remaining fully respectful of the participant's rights.

It should be clear to the participant and recorded in the trial database what aspect(s) of the trial the participant is discontinuing their participation. These could include:

- Early cessation **from questionnaires**
- Early cessation **from further trial follow-up**
- Early cessation **from electronic social care record use.**

Participants should remain in the trial for the purpose of follow-up and data analysis (unless the participant withdraws their consent from all stages of the trial). If a participant ceases follow-up early, refer to Section 5.4.

Data on participants who stop follow-up early will be kept and included in analysis, unless the participant requests their data to be deleted.

4.6 Eligibility Criteria for Individuals Performing the Interventions

The intervention will be delivered by experienced Welfare and Benefits Advisors within three months of randomisation. The UCL Researcher will arrange a WBA appointment at the participant's local CFC (where possible this will be in conjunction with the participant's 6-8 week postnatal check-up). Advice (including welfare benefits, employment, housing, debt) will be provided by LBTH's WBA and will proceed as per service standard. For straightforward cases this is a one off appointment; for others with multiple needs it may include subsequent appointments or referral to a more specialist advice service. As per service standard the advisor will work with the client until optimum financial change has been achieved. A translator will be available during advice sessions when necessary.

5 Assessments & Follow-Up

5.1 Outcomes

5.1.1 Primary Outcome(s)

Difference in depression (PHQ-8¹¹) scores at 6 months' follow-up in the intervention arm compared with the control arm accounting for baseline values and adjusted for stratification variables (if any). The outcome will be examined to ensure that it meets the assumptions for regression analyses and transformed, if necessary, to an appropriate scale so that the resultant distribution approaches normality.

5.1.2 Secondary Outcomes

Financial gain

Difference in household financial income at 6 months' follow-up in the intervention arm compared with the control arm accounting for baseline values and adjusted for stratification values (if any). The outcomes will be examined to ensure that it meets the assumptions for regression analyses and transformed, if necessary, to an appropriate scale so that the resultant distribution approaches normality.

Anxiety

Difference in GAD-7¹² scores at 6 months' follow-up in the intervention arm compared with the control arm accounting for baseline values.

Quality of life

Difference in SWEMWBS¹³ scores at 6 months' follow-up in the intervention arm compared with the control arm accounting for baseline values.

Quality of life (economic evaluation measure)

Difference in EQ-5D-5L¹⁴ scores at 6 months' follow-up in the intervention arm compared with the control arm accounting for baseline values.

5.2 Participant Timeline

Table 2: Schedule of Assessments

Visit Number	Screening	Baseline	Control Group	Intervention group	6-month follow up	Additional follow-up (subsample of participants)
Day/week	Day 0	2 weeks	1-3 months	1-3 months	6 months	6 months
Protocol visit window						
¹ Eligibility screen	X					
¹ Verbal Informed consent	X					
² Written informed e-consent		X				
² Eligibility confirmation	X	X				
Demographics data	X					
² Randomisation / Group allocation		X				
SAE review		X	X	X	X	
Interventions:						
³ Post card detailing LBTH services			X			

⁴ WBA appointment				X		
⁵ Questionnaires:						
EQ-5D-5L		X			X	
GAD-7		X			X	
PHQ-8		X			X	
SWEMWBS		X			X	
Subjective financial situation		X			X	
Self-reported household income		X			X	
⁶ Qualitative Interview						X

¹Initial eligibility screening will be performed by a health visitor and they will obtain verbal consent from interested participants for their contact details to be passed on to the UCL research team who can explain the study.

²Written informed e-consent, eligibility re-confirmation and randomisation will be performed by a UCL Researcher.

³Post card detailing LBTH services (information on where to access welfare benefits advice) to control group only.

⁴WBA appointment to be arranged for intervention group only (where possible to coincide with 6-8 week health check of newborn infant).

⁵Questionnaires will be completed at Baseline and 6-month follow-up. At each time point participants will be chased every 2 weeks for 2 months if the questionnaires have not been completed.

⁶A subsample of 45 participants from both groups will be purposively selected at random to complete an in-depth interview at 6 months.

5.3 Participant Transfers

If a participant moves address they will continue to be followed-up. Relating to participants in the intervention group (receiving WBA at the CFC) if they move address before or during receiving the intervention, every effort should be made for them to be seen by a WBA at a participating CFC which is most convenient for them.

5.4 Early Stopping of Follow-up

If a participant chooses to discontinue their trial intervention, they should always be followed up providing they are willing, that is, they should be encouraged to not leave the whole trial; if they do not wish to remain on trial follow-up, however, their decision must be respected, and the participant will be withdrawn from the trial completely. The CCTU should be informed of this in writing using the appropriate HWFinEL trial documentation. Participants stopping early may have a negative impact on trial data integrity and the ability to reach the stated endpoints.

Data already collected during the participant's participation in the trial will be kept for analysis, unless the participant requests deletion.

Participants may change their minds about stopping trial follow-up at any time and re-consent to participation in the trial. Their original randomisation allocation will stand.

Participants who withdraw from the trial will not be replaced and cannot re-enter the trial.

(See also Section 4.5 Protocol discontinuation)

5.5 Loss to Follow-up

If a participant is no longer contactable and has not completed their follow-up questionnaire within the protocol defined window, then UCL researchers should attempt to contact the participant at least three times via two different methods of contact (i.e., telephone and letter) before they are declared as lost to follow-up. We have assumed an attrition rate of 10-20% (section 8.1).

5.6 Completion of Protocol Follow-Up

Participants will complete protocol follow-up upon the completion of the questionnaire/and the in-depth interview at 6 months (if they consent to take part in this).

6 Safety reporting

This trial is very low risk as the trial intervention groups are non-invasive (i.e. money advice being offered). As such, serious adverse events are not anticipated in the HWFInEL trial; if any Serious Adverse Events (SAEs) occur to a participant during the trial, these will be recorded and appropriate action taken (i.e. intervention discontinuation or withdrawal, as deemed appropriate by the researchers).

SAEs that are **related** to the study (i.e. they resulted from any of the research procedures) and **unexpected** will be reported to the REC using the relevant documentation.

These should be sent within 15 days of the Chief Investigator becoming aware of the event.

6.1 Definitions

Definitions of harm of the European Union (EU) Directive 2001/20/EC Article 2 based on the principles of GCP apply to this trial.

Table 3: Definitions

Adverse Event (AE)	Any untoward medical occurrence in a patient or clinical trial subject to whom an intervention is being given that are not necessarily caused by or related to that product.
Serious Adverse Event (SAE)	Respectively any adverse event, adverse reaction or unexpected adverse reaction that: 
 • results in death • is life threatening* • requires hospitalisation or prolongation existing hospitalisation** • results in persistent or significant disability or incapacity • consists of a congenital anomaly or birth defect • is another significant medical condition***

* The term life threatening here refers to an event in which the patient is at risk of death at the time of the event; it does not refer to an event that might hypothetically cause death if it was more severe (e.g., a silent myocardial infarction)
 
** Hospitalisation is defined as an in-patient admission, regardless of length of stay, even if the hospitalisation is a precautionary measure for continued observation. Hospitalisation for pre-existing conditions (including elective procedures that have not worsened) do not constitute an SAE
 
*** Medical judgement should be exercised in deciding whether an AE is serious in other situations. The following should also be considered serious: important AEs that are not immediately life threatening or do not result in death or hospitalisation but may jeopardise the participant or may require intervention to prevent one of the other outcomes listed in the definition above.
	

Only events that are clearly **related** and **serious** will be considered a reportable SAE and should be reported in this study.

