1.4 Benefit Risk Assessment

The intervention plans to evaluate if there are additional benefits from receiving welfare benefit advice. There are no anticipated risks involved in participating in the intervention.

It is expected that the only risks of participation in the HWFinEL trial may be the possible unease or discomfort resulting from answering sensitive questions from the questionnaires/interviews pertaining to the participant's life. Contact information will be available for appropriate consultation should any of the material become distressing. The researchers will be alerted to scores of 10 or higher recorded on the mental health questionnaires (PHQ-8 and GAD-7) and this information will be shared with a health professional if it warrants further evaluation or support.

2 Selection of Sites/Investigators

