6.2.1 Assessment of AEs

6.2.1.1 Seriousness

When an AE occurs, the researcher responsible for the care of the participant must first assess whether or not the event is serious using the definition given in Table 3. If the event is classified as 'serious' then an SAE form must be completed and CCTU (or delegated body) notified immediately (within 24 hours).

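### Table 3's footnote on hospitalisation misplaces its worsening qualifier, so it is unclear whether admission for a worsened pre-existing condition, including depression, is an SAE

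*Protocol*

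**What the plan says.** Table 3 in Protocol Section 6.1 lists among the criteria for a serious adverse event one that "requires hospitalisation or prolongation existing hospitalisation". The double-asterisk footnote first defines the term broadly: "Hospitalisation is defined as an in-patient admission, regardless of length of stay, even if the hospitalisation is a precautionary measure for continued observation". It then narrows the criterion: "Hospitalisation for pre-existing conditions (including elective procedures that have not worsened) do not constitute an SAE".

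Section 6.2.1.1 makes Table 3 the first step for any adverse event. If the event is classed as serious, "then an SAE form must be completed and CCTU (or delegated body) notified immediately". Section 6.2.1.2 requires a causality assessment for serious events, and Section 6.2.1.4 (Expectedness) adds an expectedness review where the intervention or comparator may be involved. The opening of Section 6 promises that "if any Serious Adverse Events (SAEs) occur to a participant during the trial, these will be recorded and appropriate action taken". The schedule in Section 5.2 (Table 2) contains an SAE review and no general adverse event review.

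Depression, measured by PHQ-8, is the primary outcome (Section 5.1.1), and anxiety is a secondary outcome (Section 5.1.2). The eligibility criteria in Sections 3.1 and 3.2 do not exclude parents with current or past depression or anxiety. Section 1.4 provides for raised scores: "The researchers will be alerted to scores of 10 or higher recorded on the mental health questionnaires (PHQ-8 and GAD-7".

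**The concern.** The footnote appears to be a version of a common exclusion: an admission for a condition the participant already had, and which is no worse, is not counted as a new serious event. As punctuated, it does not say that. The words about worsening fall inside the bracket and qualify elective procedures, while the main clause excludes admissions for pre-existing conditions without limit.

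This matters more here than in many trials because the condition most likely to be caught is the one under study. Parents with existing depression or anxiety may enrol, and worsening mental health is the harm closest to the primary outcome. The classification is made by a researcher, on events that CFC staff may be the first to hear of (Sections 6.2 and 6.2.1.1). There is no separate data monitoring committee; the TSC takes on that function (Section 16.3) and relies on what has been recorded. A definition that two careful readers can apply in opposite ways is a weak basis for that oversight.

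**Working it through.** No arithmetic applies. The check sets the two readings of the footnote against the types of admission that could arise, and then follows the consequences through the protocol.

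**Step 1: the two readings.**
- *Literal:* the qualifier belongs to elective procedures, and every admission for a pre-existing condition is outside the hospitalisation criterion.
- *Probably intended:* the qualifier belongs to the pre-existing condition, and only admissions for an unworsened condition are outside it. A procedure cannot worsen, so the qualifier has meaning only on this reading.

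**Step 2: classification under each reading.**

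| Admission | Literal reading | Probably intended reading |
|---|---|---|
| New condition, including new-onset depression | SAE | SAE |
| Planned elective procedure, pre-existing condition unchanged | Not an SAE | Not an SAE |
| Worsened pre-existing depression, risk of death at the time | SAE, by the life-threatening criterion | SAE |
| Worsened pre-existing depression, not life-threatening | Fails the hospitalisation criterion; serious only if another criterion or medical judgement applies | SAE |

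The readings part only in the last row. The same holds for anxiety or any other condition present before entry.

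**Step 3: what follows for that last row.**
- Section 6.2.1.1: the SAE form is triggered by a serious classification. Literal reading: not triggered. Intended reading: triggered.
- Section 6.2.1.2: causality is assessed for serious events. Literal: not required. Intended: required.
- Section 6.2.1.4 (Expectedness): this arises only after causality has been judged at least possible, so on the literal reading the question is not reached.
- Section 5.2 and the opening of Section 6: the scheduled review and the recording promise both concern SAEs, so neither gives a non-serious event a stated route into the safety data.

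**Step 4: does another section settle the reading?** None does. Sections 6.2 to 6.2.1.4 all refer back to the classification in Table 3 or start from it.

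**The case against.** The case against making much of this is a fair one, and several parts of it stand.

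- **The qualifier is present.** A reader might infer that the protocol makes no exception for worsening. It does contain the words, in the wrong place, and the sensible reading is the usual one. This is a drafting fault, not a decision to ignore worsening. That stands. It does not remove the fault, because the literal wording points the other way.
- **Other routes to serious remain.** A reader might infer that an admission for worsened depression leaves no trace in the safety data. That does not follow. The footnote limits only the hospitalisation criterion. Death, disability and the life-threatening criterion, defined as "an event in which the patient is at risk of death at the time of the event", are unaffected. There is also a general clause: "Medical judgement should be exercised in deciding whether an AE is serious in other situations". That clause is a weaker route here, because the important events it goes on to describe are ones that did not lead to hospitalisation.
- **Mental health is measured anyway.** PHQ-8 and GAD-7 are collected in both arms at baseline and 6 months, and scores of 10 or higher raise an alert. True, but a questionnaire score at two time points does not record an admission between them.
- **Reportability is limited on either reading.** Section 6.1 confines reportable SAEs to events that are both clearly related and serious, so an unrelated admission would not be reportable however the footnote is read. This stands. What the footnote changes for such an event is whether the form and causality entry are completed at all.
- **Harms could not be empty by construction.** A reader might infer that the safety report is bound to show no events. It is not: new-onset conditions, life-threatening events and deaths all still count.

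**Conclusion.** The footnote is wrong as written and the point is minor. It gives opposite classifications to one kind of event: a non-life-threatening admission for worsening of a condition present before entry. For that event, whether an SAE form and causality assessment are required depends on how the reader parses a bracket, unless another seriousness criterion or medical judgement brings it in.

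The size cannot be estimated. The protocol gives neither the baseline prevalence of depression or anxiety nor an admission rate. Applying an assumed prevalence to the 1153 participants would count people with a history, not admissions, so it would not measure the effect. The number of affected admissions may be small. The primary analysis does not use SAE data and is unaffected.

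The conclusion rests on the punctuation of the footnote, on no other section resolving it, and on the eligibility criteria admitting parents with existing depression or anxiety. It does not assume that staff will adopt the literal reading, only that the text permits it.

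**What to change.** Reword the sentence so that it has one meaning, for example: *Hospitalisation for a pre-existing condition that has not worsened since consent (including planned elective procedures) does not constitute an SAE.* An admission because a pre-existing condition has worsened, depression and anxiety included, is then assessed as an SAE under the hospitalisation criterion. Carry the same wording into the SAE form guidance, so that researchers and CFC staff apply one rule.

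The cost is one sentence in a protocol amendment and a matching line in the form guidance. The downside is a few more SAE forms to complete and assess for causality. The limit on which SAEs are reportable need not change.

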6.2 Investigator responsibilities

SAEs should be notified to CCTU immediately and no later than **24 hours** after the CFC staff becomes aware of the event by email to the HWFinEL trial team using the trial specific SAE form.

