6.2.1.2 Causality

The researcher must assess the causality of all serious events in relation to the trial intervention using the definitions in Table 4. There are five categories: unrelated, unlikely, possibly, probably, and definitely related. If the causality assessment is unrelated or unlikely to be related, the event is classified as an '**unrelated SAE**'. If the causality is assessed as possibly, probably or definitely related, then the event is classified as a '**related SAE**'.

Table 4: Assigning Causality

Relationship	Description
Definitely	There is clear evidence to suggest a causal relationship and other possible contributing factors can be ruled out
Probably	There is evidence to suggest a causal relationship and the influence of other factors is unlikely
Possibly	There is some evidence to suggest a causal relationship (e.g., because the event occurs within a reasonable time after administration of the trial intervention). However, the influence of other factors may have contributed to the event (e.g., the participant's clinical condition, other concomitant events)
Unlikely	There is little evidence to suggest that there is a causal relationship (e.g., the event did not occur within a reasonable time after administration of the trial intervention). There is another reasonable explanation for the event (e.g., the participant's clinical condition, other concomitant event)
Unrelated	There is no evidence of any causal relationship

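### Section 6.1 limits SAE reporting to 'clearly related' events, contradicting the 24-hour notification of every serious event in 6.2 and 6.2.1.1 and the 'possibly related' threshold in 6.2.1.2 and 6.2.1.4

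*Protocol*

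**What the plan says.** All of this is in protocol section 6 and its subsections.

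- **Section 6, introduction.** Recording has no causality condition: "if any Serious Adverse Events (SAEs) occur to a participant during the trial, these will be recorded and appropriate action taken". A separate onward tier follows: SAEs that are both related and unexpected "will be reported to the REC using the relevant documentation", within 15 days of the Chief Investigator becoming aware.
- **Section 6.1, after Table 3.** Only serious events that are clearly related "will be considered a reportable SAE and should be reported in this study".
- **Section 6.2.** "SAEs should be notified to CCTU immediately and no later than" 24 hours after site staff become aware. No causality condition is attached.
- **Section 6.2.1.1.** Seriousness is assessed first. If the event is serious, "then an SAE form must be completed and CCTU (or delegated body) notified immediately (within 24 hours"). Again there is no causality condition.
- **Section 6.2.1.2 and Table 4.** Causality is assessed for all serious events on five grades. "If the causality is assessed as possibly, probably or definitely related", the event is a related SAE; the two lower grades make it an unrelated SAE.
- **Section 6.2.1.4 (Expectedness).** From possible involvement of the intervention or comparator upwards, a clinical reviewer delegated by CCTU assesses expectedness.
- **Section 16.3.** There is no separate IDMC; the TSC takes on the data-monitoring function.

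**The concern.** A researcher who reads 6.1 as the operative rule would send CCTU only those serious events judged clearly caused by the study. One who reads 6.2.1.1 would send all of them. Both would be following the protocol.

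The REC duty is where this matters most. Expectedness is judged centrally, so an event has to reach CCTU before anyone can decide whether it is unexpected and must go to the REC. A filter at site that is stricter than the protocol's own definition of related cuts that chain at its first link. The TSC, as the only body with a data-monitoring role, would also be working from incomplete reports.

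**Working it through.** No alpha, power, rate or sample size enters this point, and the plan gives no figure to reproduce. The check applies each rule to the five causality grades of Table 4.

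| Table 4 grade | Form and 24-hour notice to CCTU (6.2.1.1, and 6.2 as worded) | Related SAE (6.2.1.2) | Expectedness review (6.2.1.4) | Reportable (6.1) |
|---|---|---|---|---|
| Definitely | yes | yes | yes | yes |
| Probably | yes | yes | yes | unclear |
| Possibly | yes | yes | yes | no, on plain wording |
| Unlikely | yes | no | no | no |
| Unrelated | yes | no | no | no |

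The last column needs an assumption, because 6.1 does not define 'clearly'. The only Table 4 description that uses the word 'clear' is the one for Definitely, which gives one reportable grade. 'Probably' is described as having other influences unlikely, so a reader could include it, which gives two.

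- Grades notified under 6.2.1.1 but not reportable under 6.1: 5 − 1 = 4, or 5 − 2 = 3.
- Grades that 6.2.1.2 calls related but 6.1 leaves out: 3 − 1 = 2, or 3 − 2 = 1.
- If 'clearly' were deleted and 6.1 used the related class of 6.2.1.2: 5 − 3 = 2 grades would still be in conflict with 6.2.1.1.

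**One event traced through.** Take a serious event judged possibly related that is in fact unexpected. Section 6.2.1.1 requires the form within 24 hours. Section 6.2.1.2 makes it a related SAE. Section 6.2.1.4 sends it to the central reviewer, and the section 6 introduction then requires a REC report. Section 6.1 says it is not reportable. If the researcher stops at 6.1, the central reviewer may not hear of it, and the 15-day period, which runs from the Chief Investigator's awareness, may never start.

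**Two readings that might reconcile the text.**

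1. Section 6.1 describes the REC tier. This fails: the section 6 introduction already sets the REC rule on different terms (related and unexpected), and 6.1 speaks of reporting in the study.
2. 'SAEs' in 6.2 means only the reportable SAEs of 6.1. This could rescue 6.2, but not 6.2.1.1, which ties the form and the 24-hour limit to seriousness alone.

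**The case against.** The best case on the other side is that this is one badly worded sentence in a very low-risk trial of money advice. Section 6 does not anticipate SAEs, safety is not among the outcomes in section 5.1, and section 1.4 provides a separate alert for PHQ-8 and GAD-7 scores of 10 or higher. Section 6.2.1.2 is a classification and not a notification rule, so the protocol does not contain three rival notification rules. All of that stands, and it limits the weight of the point. It does not remove the clash between 6.1 and 6.2.1.1, or the mismatch between 'clearly related' and the related class that drives expectedness review and REC reporting. Low risk may justify a narrow rule, but the protocol would then have to state that rule consistently.

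A reader might also draw three stronger conclusions that the document does not support.

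- *That safety data will not be comparable between the arms.* Researchers are unblinded (section 4.4), and 6.2.1.2 judges causality against the trial intervention, so unequal reporting is possible. But section 6 defines related as resulting from any research procedure, 6.2.1.4 includes the comparator, and both arms complete the same questionnaires, which section 1.4 names with the interviews as the only expected source of risk. No between-arm safety comparison is stated in the protocol. This is a possible risk and no more.
- *That the causality and expectedness reviews would have nothing to act on.* Causality is graded for every serious event before any relatedness filter can be applied, and events that pass even the narrowest filter would still reach expectedness review.
- *That events would be lost altogether.* The section 6 introduction requires all SAEs to be recorded, and Table 2 schedules SAE review at baseline, in both arm columns and at 6 months (though not at screening or the additional interview follow-up).

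**Conclusion.** The contradiction is real and lies in the current text. Section 6.1 cannot be followed together with 6.2.1.1, and its threshold disagrees with 6.2.1.2 and 6.2.1.4. Three or four of the five causality grades are affected for notification to CCTU, and one or two of the three grades that the protocol itself calls related. The range depends only on whether 'clearly' is taken to include Probably.

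The practical consequence is conditional: if staff apply 6.1, related and unexpected SAEs might miss the expectedness review and the REC report, and the TSC would see incomplete reports. How many events this would touch cannot be derived from the protocol. The primary analysis is not affected. This should be corrected as a wrong safety-reporting rule; it is not a matter of missing detail that could be left to a SAP.

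**What to change.** Reconcile the section 6 introduction, 6.1, 6.2, 6.2.1.1, 6.2.1.2 and 6.2.1.4 (Expectedness) into one scheme that states separately, and identically for both arms:

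1. which events are recorded;
2. which are notified to CCTU on an SAE form, and by when;
3. which go on to the REC.

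Wherever relatedness is the criterion, refer to the related SAE class of 6.2.1.2 and avoid an undefined term. Deleting 'clearly' from 6.1 is not sufficient, because 6.1 would still restrict reporting to related events while 6.2 and 6.2.1.1 call for all serious ones. Which notification rule applies is for the sponsor to decide.

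The cost is a protocol wording amendment, with the site instructions brought into line. No new data collection is needed for the scheduled contacts, because Table 2 already includes SAE review for both arms.
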